**Table 21: Sample Size Calculation for Each Cohort: Comparing to a Known Proportion**

Tumor Type	ORR		Sample Size
	H0	Ha	
NSCLC high positive (PD-L1 TPS $\geq$ 50%)	36%	56%	42
NSCLC low/negative or indeterminate (PD-L1 TPS 0%-49% or indeterminate)	12%	32%	25
Melanoma (immune checkpoint-naïve)	32%	52%	40
Transitional cell carcinoma of the GU tract	24%	44%	36
TNBC	19%	39%	32
Ovarian cancer	20%	40%	33
SCCHN	19%	39%	32
DLBCL	36%	57%	37
RCC	25%	45%	36
MSI high CRC	57%	80%	29
Gastric cancer	14%	34%	27
HCC	19%	39%	32
Melanoma (primary refractory)	3%	20%	27 a
Melanoma (relapsed)	10%	35%	18 a
Total			446

a Maximum possible sample size for Simon 2-stage design. Actual sample size may be less.

### 9.3. Level of Significance

The level of significance for the primary endpoint in Phase 2 is one-sided 5%, which is deemed acceptable for a proof-of-concept study.

### 9.4. Statistical Analyses

#### 9.4.1. Primary Analyses

Primary efficacy analysis will be conducted for the Phase 2 efficacy evaluable population. The primary variable for the Phase 2 expansion portion of the study is ORR, which is defined as the proportion of subjects with best response (CR or PR) by irRECIST v1.1 for select solid tumors and modified Lugano Classification (Cheson et al 2014) for DLBCL. The 95% exact CI for the ORR will be estimated using the Clopper-Pearson method. One sample binomial test will be used to test the null hypotheses.

#### 9.4.2. Secondary Analyses

Secondary efficacy analysis will be conducted for the efficacy evaluable population.

Progression-free survival is defined as number of days from the first day of taking study drug to the earlier of death or disease progression by irRECIST v1.1 for select solid tumors and modified Lugano Classification (Cheson et al 2014) for DLBCL. Time-to-event data will be analyzed by the Kaplan-Meier method, treating subjects with no observed death or progression as censored at

their last valid response assessment or last valid response assessment date prior to post study cancer treatment. For the OS analysis, the nonparametric Kaplan-Meier method will be used to estimate the survival time distribution and the median survival of each tumor type.

For objective responders, the duration of response is the time from the first objective response contributing to an objective response, to the first objective response of PD (by irRECIST v1.1) occurring after the first objective response contributing to the objective response. Median duration of response will be estimated using the Kaplan-Meier method. The duration of disease control is the time from the treatment start date to the first objective response of PD (by irRECIST v1.1 or Lugano Classification ([Cheson et al 2014](#)) occurring after the first objective response of CR/PR/SD. Median duration of disease control will be estimated using the Kaplan-Meier method.

The ordinal response scores are defined as the following:

- 1 = Complete response per irRECIST v1.1
- 2 = Very good response, defined as > 60% tumor reduction
- 3 = Minor response, defined as >30% to ≤ 60% tumor reduction
- 4 = Stable disease per irRECIST v1.1
- 5 = Progressive disease per irRECIST v1.1

The frequency of subjects in each category will be summarized by tumor type.

For OS analysis, the Kaplan-Meier method will be used to estimate the survival time distribution and the median survival of each tumor type.

### **9.4.3. Safety Analyses**

The principal analysis will be based on the safety evaluable population, according to treatment assignment.

Adverse events will be coded by the MedDRA, and incidences will be tabulated by preferred term and system organ class for all events, related events, events ≥ Grade 3 and adverse events of special interest. Severity of AEs will be based on the CTCAE scale as indicated in Section 8.1.1. Quantitative safety variables and their changes from baseline (laboratory, vital signs) will be summarized with descriptive statistics. Clinically significant abnormal values will be flagged and tabulated based on predefined criteria.

Exposure will be analyzed by describing dose intensity, which is defined as the dose-received divided by the dose planned over a given time interval. This will be done by cycle as well as overall cycles received for MK-3475 + INCB024360. The percentage of subjects with any delay and/or reduction will also be calculated.

The clinical laboratory data will be analyzed using summary statistics (eg, means and frequencies), and no formal statistical comparisons among the treatments are planned. In addition, these values will also be classified into CTCAE toxicity grades and tabulated. Descriptive statistics and mean change from baseline will be determined for vital signs at each assessment time. Vital sign results will be reviewed for clinically notable abnormalities.

## 9.5. Data Monitoring Committee

Not applicable.

## 9.6. Interim Safety Analyses

An interim safety analysis is planned for Phase 2 after 20 subjects have been enrolled and treated for 9 weeks, and then approximately every 3 months thereafter. If the following is reported during these reviews, enrollment of subjects would be suspended until the sponsor(s), investigators, and regulatory authorities, if applicable, have determined the appropriate course of action:

- > 40% of subjects have had an AE  $\geq$  Grade 3 that was attributable to the investigational agents.

Based on these rules, the probabilities of stopping a treatment group for safety is provided in [Table 22](#).

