### **1.3.3. Risks for the Combination of INCB024360 and MK-3475**

The combination of INCB024360 and MK-3475 has the potential to cause more frequent, more severe, and/or new immune-related toxicities as compared with each individually.

In this ongoing Phase 1/2 study combining pembrolizumab and epacadostat, preliminary data suggest that doses up to 300 mg BID of epacadostat are well tolerated with pembrolizumab 200 mg IV. While 300 mg BID did not exceed the MTD, preliminary analysis of 19 subjects suggested that there were higher rates of dose holds and reductions compared to 100 mg BID, supporting 100 mg BID as the Phase 2 dose (as detailed later in this section). In the Phase 1 portion of the study, a DLT of Grade 3 rash and Grade 3 arthralgia were seen in 2 of 19 evaluable subjects treated with epacadostat 50 mg BID; 2 DLTs in 15 evaluable subjects were seen with epacadostat 100 mg BID (Grade 3 AST and Grade 2 nervous system disorder,

other – ataxia), and 4 DLTs in 19 evaluable subjects were seen at 300 mg BID (Grade 1 erythema, 2 Grade 3 rashes and 1 nervous system disorder – other – vomiting without nausea).

Among the 294 subjects who have received epacadostat 100 mg BID in combination with pembrolizumab in Phase 2, the most frequently reported ( $\geq 5\%$ ) treatment-related AEs were fatigue (29%), rash (17%), nausea (11%), pruritus (10%), diarrhea (8%), decreased appetite (7%), and arthralgia (6%). Rash (17%) noted above includes the following preferred terms: rash, rash maculopapular, rash generalized, rash pruritic, and rash macular. Grade 3 or higher treatment-related AEs were reported in 18% of subjects. Treatment-related AEs leading to treatment discontinuations occurred in 11 subjects (4%); the most common were arthralgia and rash (n = 2 subjects each); others occurred in 1 subject each. There was 1 treatment-related death due to respiratory failure (secondary to aspiration pneumonia; pneumonitis could not be ruled out).

Any treatment-related Grade 3/4 AEs occurring in more than 1 subject included lipase increased (n = 12, 4%), rash (n = 9, 3.0%); fatigue, diarrhea, amylase increased (n = 4 each, 1%); ALT increased and AST increased (n = 2 each, 1%) (Hamid et al 2017).

As noted in Section 1.1.4, the eDMC review of the Phase 3 randomized study ECHO-301/KEYNOTE-252 study noted the safety profile observed was consistent with that observed in previously reported studies of INCB024360 in combination with MK-3475.

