#### 4.1.2. Phase 2 Cohort Expansions

The purpose of the cohort expansions is to gather additional safety, tolerability, preliminary efficacy, [REDACTED] information regarding the combination of INCB024360 and MK-3475 200 mg. Once the safety profile of all doses tested has been characterized and the RP2D of combined administration of INCB024360 and MK-3475 has been defined, the cohort expansions will be initiated at the RP2D (determined in Phase 1 to be 100 mg BID). Fourteen expansion cohorts will be restricted to NSCLC (2 cohorts: PD-L1 positive and PD-L1 low/negative or indeterminate), melanoma (3 cohorts: checkpoint-naïve, primary refractory and relapsed), transitional cell carcinoma of the GU tract, TNBC, SCCHN, ovarian cancer, DLBCL, MSI high CRC, clear cell RCC, gastric cancer, and HCC. Continuous evaluation of toxicity events in the cohort expansions will be performed throughout enrollment in the expansion cohorts (see [Section 9.6](#)). If the rate of DLTs exceeds 40%, the findings will be reviewed and further enrollment may be interrupted until the sponsor(s), investigators, and regulatory authorities, if applicable, have determined the appropriate course of action. If an expansion

cohort is discontinued due to toxicity, a new cohort may be initiated at a previously tested lower dose level.

In each of the cohorts, approximately 18 to 42 subjects will be enrolled to allow for a more precise estimate of ORR in subjects with these tumors and determine whether a target response rate (20%-62%) is likely (Table 3).

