**Table 22: Probability of Early Termination for Various Safety Event Rates**

Proportion of Subjects Having an AE <math>\geq</math> Grade 3 That Was Attributable to the Investigational Agent	Probability of Early Termination Based on an AE <math>\geq</math> Grade 3 That Was Attributable to the Investigational Agenta
5%	0.0%
10%	0.04%
15%	0.58%
20%	3.17%
25%	10.35%
30%	24.31%
40%	85.37%

a The probability of early termination = Prob ( $\geq$  40% of subjects in the active treatment group have had an AE  $\geq$  Grade 3 at the first interim safety analysis OR at the second interim OR at the third interim OR at the fourth interim).

No formal interim analysis for futility or efficacy is planned for this study.

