9.2. Guidelines for Decision Rules

An interim safety analysis is planned for Phase 2 after 20 subjects have been enrolled and treated for 9 weeks, and then every 3 months thereafter. If the following is reported during these reviews, then enrollment of subjects would be suspended until the sponsor(s), investigators, and regulatory authorities, if applicable, have determined the appropriate course of action:

• > 40% of subjects have had an AE \geq Grade 3 that was attributable to the investigational agent.

Based on these rules, the probabilities of stopping a treatment group for safety is provided in Table 13.

 Table 13:
 Probability of Early Termination for Various Safety Event Rates

Proportion of Subjects Having an AE ≥ Grade 3 That Was Attributable to the Investigational Agent	Probability of Early Termination Based on an AE ≥ Grade 3 That Was Attributable to the Investigational Agent ^{ab}
5%	0.0%
10%	0.1%
15%	0.6%
20%	3.3%
25%	10.2%
30%	23.3%
40%	80.7%

^a Assumes the interim safety analyses occur when enrollment is 20, 80, 160, 240, and 276, etc, subjects. Probability estimated via simulation with 100,000 replications.

^b The probability of early termination = Prob (($\geq 40\%$ of subjects in the active treatment group have had an AE \geq Grade 3 at the first interim safety analysis OR at the second interim OR at the third interim OR at the fourth interim).

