10.1. Changes to Protocol-Defined Analyses

Study enrollment was permanently discontinued on 17 MAY 2018 as a strategic decision. This decision was made following the recommendation of the external Data Monitoring Committee of the INCB 24360-301 blinded melanoma clinical study, which determined that the study did not meet the prespecified endpoint of progression-free survival improvement for the combination of pembrolizumab + epacadostat compared with pembrolizumab + placebo; in addition, the overall survival (OS) endpoint was not expected to reach statistical significance. Of note, there were no new safety concerns identified in either arm of the melanoma study.

Due to this strategic decision, Protocol-defined analyses were reduced. Efficacy analyses will only be performed for primary and secondary endpoints

See Appendix E for a detailed list of outputs that will be included in the abbreviated CSR for both safety and efficacy.

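### The Phase 2 safety suspension rule is written as more than 40%, but the stopping probabilities printed for it are those of at least 40%, and the Protocol and SAP tables disagree

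*Protocol*

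**What the plan says.** **The rule.** Protocol 9.6 suspends enrollment, pending a decision on what to do, if "> 40% of subjects have had an AE" of Grade 3 or higher attributable to the study agents. Protocol 5.5.3 and SAP 9.2 give the same threshold with the same strict inequality. The first look comes once 20 subjects have been enrolled and treated for 9 weeks; later looks follow about every 3 months.

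**The tables.** Both documents present a table of stopping probabilities as following from this rule; the Protocol wording is "Based on these rules, the probabilities of stopping a treatment group for safety is provided in" Table 22. The footnote to Table 22 reads "The probability of early termination = Prob ( $\geq$ 40% of subjects in the active treatment group", and footnote b of SAP Table 13 reads "The probability of early termination = Prob (($\geq 40\%$ of subjects in the active treatment group". Both footnotes run from the first to the fourth interim.

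**The look schedule.** Only the SAP gives look sizes. Footnote a of Table 13: "Assumes the interim safety analyses occur when enrollment is 20, 80, 160, 240, and 276, etc, subjects". It states that the probabilities were simulated with 100,000 replications. Planned Phase 2 enrollment is 446 (Protocol Table 21, SAP Table 4).

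**Context.** Protocol 4.1.2 has a separate trigger, "If the rate of DLTs exceeds 40%, the findings will be reviewed and further enrollment may be interrupted", with no stated probabilities. Protocol 1.3.3, on 294 Phase 2 subjects, says "Grade 3 or higher treatment-related AEs were reported in 18% of subjects". SAP 10.1 records that "Study enrollment was permanently discontinued on 17 MAY 2018 as a strategic decision".

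**The concern.** The text and the footnotes define two different rules, and the tables can belong to only one of them. The inequality matters because the first look falls at 20 subjects, where exactly 40% is a whole number of events. Eight events suspend enrollment under one reading and not under the other.

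This is the only Phase 2 safety rule for which the plan states operating characteristics, and Protocol 8.8 provides no formal data monitoring committee. The rows below a true rate of 40% show how often enrollment would be suspended although toxicity is below the threshold, and proportionally those rows depend most on the inequality. The two tables carry the same event definition yet print different values, so a reader cannot tell which is correct.

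**Working it through.** **Inputs.** Threshold 40%, with either inequality. First look at n = 20 (Protocol 9.6). Look sizes 20, 80, 160, 240, 276 (SAP Table 13, footnote a). Three schedules were run:
- A: 20/80/160/240 (the four interims of the footnotes)
- B: A plus 276 (the SAP list)
- C: B plus 320/400/446. The last three sizes are an assumption, because the SAP says only etc.

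**Method.** Let X be the number of subjects with an event among n. Between looks, X grows by a binomial increment with true rate p. At each look, paths with X/n at or over the boundary (X/n ≥ 0.40, or X/n > 0.40) are removed and their probability is added to the stopping total. The calculation is exact, with no simulation.

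**Step 1: first look alone.** X ≥ 8 of 20 against X ≥ 9 of 20:

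| True rate | ≥ 40% | > 40% |
|---|---|---|
| 20% | 3.21% | 1.00% |
| 25% | 10.18% | 4.09% |
| 30% | 22.77% | 11.33% |
| 40% | 58.41% | 40.44% |

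**Step 2: reproduce the printed figures.** All looks:

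| True rate | Protocol Table 22 | SAP Table 13 | Exact, ≥ 40% | Exact, > 40% |
|---|---|---|---|---|
| 10% | 0.04% | 0.1% | 0.04% | 0.006% |
| 15% | 0.58% | 0.6% | 0.59% | 0.13% |
| 20% | 3.17% | 3.3% | 3.22% | 1.00% |
| 25% | 10.35% | 10.2% | 10.26% | 4.15% |
| 30% | 24.31% | 23.3% | 24.10% | 12.47% |
| 40%, schedule A | 85.37% | 80.7% | 82.35% | 73.02% |
| 40%, schedule B | 85.37% | 80.7% | 83.39% | 75.45% |
| 40%, schedule C | 85.37% | 80.7% | 86.79% | 80.40% |

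Up to the 30% row, the choice among A, B and C moves the exact values by no more than 0.01 points. In those rows the printed values follow at least 40%.

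**Step 3: ratio of printed to exact if more than 40% is the rule.**
- Protocol: 3.17/1.00 = 3.17; 10.35/4.147 = 2.50; 24.31/12.47 = 1.95.
- SAP: 3.3/1.00 = 3.30; 10.2/4.147 = 2.46; 23.3/12.47 = 1.87.

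**Step 4: is the disagreement between the tables simulation error?** Take at least 40%, schedule B and 100,000 replications.
- At a true rate of 40%, the standard error is √(0.8339 × 0.1661 / 100,000) = 0.12 points. The SAP's 80.7% is 2.69 points below 83.39%, about 23 standard errors.
- At 30%, the standard error is √(0.2410 × 0.7590 / 100,000) = 0.135 points. The SAP's 23.3% is 0.80 points below 24.10%, about 6 standard errors.

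So SAP Table 13 does not match its own footnotes at its own listed looks. Its 40% entry lies below the whole range for at least 40% (82.35 to 86.79%). It is within 0.3 points of the value for more than 40% on schedule C. That closeness rests on assumed looks and on the opposite inequality to the one its lower rows follow, so it does not show how the figure was obtained.

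**Step 5: at the reported rate of 18%.** The stopping probability is 0.49% (more than) or 1.77% (at least), whichever schedule is used.

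**The case against.** The strongest reply has four parts.

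- **The gap is a tie effect at n = 20.** The inequalities differ only when exactly 40% is attainable. With a first look at 21 and later looks at 80/160/240, they almost coincide: 1.44 against 1.44% at a true rate of 20%, 5.66 against 5.72% at 25%, and 15.71 against 16.53% at 30% (more than, at least). This is correct, and the ratios above hold only for a first look at exactly 20. But 20 is the size both documents name, and it is the first look the SAP's calculation assumes.
- **The Protocol gives no later look sizes.** Applying the SAP's sizes to Table 22 is an assumption. With looks at 20/40/60/80, more than 40% gives 4.70% at 25% and 15.09% at 30%, so the Protocol ratios fall to 2.20 and 1.61. They remain well above 1.
- **The tables barely differ up to the 25% row.** True: by at most 0.15 points there. The visible differences are 1.0 point at 30% and 4.7 points at 40%. Unstated Protocol assumptions may explain part of this, which is itself a reason to state them.
- **Little now depends on it.** Suspension leads to discussion rather than automatic termination, enrollment has ended, and SAP Appendix E plans no stopping-probability output. This stands, and it limits the point to accurate description of the rule.

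**Conclusion.** The concern holds. The stated probabilities do not belong to the stated rule. If more than 40% is kept, both tables overstate the chance of suspension at true rates of 20, 25 and 30% by factors of about 3.2, 2.5 and 1.9. If at least 40% is kept, Table 22 is within about 0.3 points up to the 30% row, and its 40% entry lies within the range across schedules A to C, although not at the four looks its footnote counts (82.35% against 85.37%). SAP Table 13 would still need correction at 30 and 40%. Whichever inequality is retained, the tables conflict with each other and the look schedule is undefined: five looks plus etc in one footnote, four in the other two.

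The factors assume a first look at exactly 20 and the SAP's later look sizes. Looks beyond 276 are assumed and affect only the 40% row materially. No efficacy estimate or test is touched, and at the reported 18% rate either reading makes suspension unlikely.

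**What to change.** - Reconcile the inequality between the rule text (Protocol 5.5.3 and 9.6, SAP 9.2) and the footnotes to Protocol Table 22 and SAP Table 13. Which threshold applies is for the sponsor to state; this review does not choose.
- State one look schedule that reaches planned enrollment, replacing both the open-ended list and the count of four interims.
- Recompute one table exactly for the retained rule and schedule, and print the same table in Protocol 9.6 and SAP 9.2. With enrollment closed, correcting the SAP and the description of the rule in the clinical study report would be enough.

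The cost is one short calculation and text edits in two documents.

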**Table 22: Probability of Early Termination for Various Safety Event Rates**

Proportion of Subjects Having an AE <math>\geq</math> Grade 3 That Was Attributable to the Investigational Agent	Probability of Early Termination Based on an AE <math>\geq</math> Grade 3 That Was Attributable to the Investigational Agenta
5%	0.0%
10%	0.04%
15%	0.58%
20%	3.17%
25%	10.35%
30%	24.31%
40%	85.37%

a The probability of early termination = Prob ( $\geq$  40% of subjects in the active treatment group have had an AE  $\geq$  Grade 3 at the first interim safety analysis OR at the second interim OR at the third interim OR at the fourth interim).

No formal interim analysis for futility or efficacy is planned for this study.

## 10. STUDY DRUG MATERIALS AND MANAGEMENT

### 10.1. Investigational Products Description

#### 10.1.1. Packaging, Labeling, and Preparation of Study Drug

##### 10.1.1.1. INCB024360

The study drug will be available as 25 mg and 100 mg tablets packaged in high-density polyethylene bottles. All tablet excipients comply with the requirements of the applicable compendial monographs (Ph. Eur., USP/NF) (refer to the [iIB](#)). All Incyte investigational product labels will be in the local language and will comply with the legal requirements of each country.

##### 10.1.1.2. MK-3475

The investigator shall take responsibility for and shall take all steps to maintain appropriate records and ensure appropriate supply, storage, handling, distribution and usage of investigational product in accordance with the Protocol and any applicable laws and regulations. Clinical supplies will be provided by Merck as summarized in [Table 23](#).

**Table 23: MK-3475 Product Descriptions**

Product Name and Potency	Dosage Form
MK-3475 100 mg/4 mL	Solution for Injection

Clinical supplies will be affixed with a clinical label in accordance with regulatory requirements.

#### 10.1.2. Storage and Stability of Study Drugs

##### 10.1.2.1. INCB024360

Clinical supplies must be stored as described in the [iIB](#).

##### 10.1.2.2. MK-3475

Clinical supplies must be stored in a secure, limited-access location under the storage conditions specified on the label. Receipt and dispensing of study drug must be recorded by an authorized person at the study site. Clinical supplies may not be used for any purpose other than that stated in the Protocol.

## 10.2. Accountability, Handling, and Disposal of INCB024360 and MK-3475

Responsibility for drug accountability at the study site rests with the investigator; however, the investigator may assign some of the drug accountability duties to an appropriate pharmacist or other designee. Inventory and accountability records must be maintained and readily available for inspection by the study monitor and are open to inspection at any time by any applicable regulatory authorities.

The investigator or designee will be expected to collect and retain all used, unused, and partially used containers of study drug according to their institution policies. The investigator or designee must maintain records that document:

- Delivery of study drug to the study site.
- Inventory of study drug at the site.
- Subject use of the study drug including pill or unit counts from each supply dispensed.
- Return of study drug to the investigator or designee by subjects.

These records should include dates, quantities, batch or serial numbers (if available), and the unique code numbers (if available) assigned to the investigational product and study subjects.

The investigational product must be used only in accordance with the Protocol. The investigator will also maintain records adequately documenting that the subjects were provided the correct study drug specified.

Completed accountability records will be archived by the site. At the completion of the study, the investigator or designee will oversee shipment of any remaining INCB024360 back to the sponsor or its designee for destruction according to institutional standard operating procedures. If local procedures mandate site destruction of investigational supply, prior written approval must be obtained from Incyte.

Upon completion or termination of the study, all unused and/or partially used MK-3475 will be destroyed at the site per institutional policy. It is the investigator's responsibility to arrange for disposal of all empty containers, provided that procedures for proper disposal have been established according to applicable federal, state, local, and institutional guidelines and procedures, and provided that appropriate records of disposal are kept.

